# **Study Overview**

## Introduction

This Statistical Analysis Plan (SAP) outlines the statistical methodologies and procedures for analysing data from the RE.PROCESS study, a four-armed randomized controlled trial. Three trauma-focused therapies (Prolonged Exposure [PE], Eye Movement Desensitization and Reprocessing [EMDR], and Cognitive Restructuring [CR]) are compared to a waitlist control group (WL) in individuals with co-occurring posttraumatic stress disorder (PTSD) and lifetime psychotic disorder. Primary and secondary outcomes are measured at baseline (T0), mid-treatment (T2) at 7 weeks, posttreatment (T3) at 3 months, and 6-month follow-up (T6). An extensive study protocol, including information on rationale, participants, and interventions, is published elsewhere.

#### Study Design

This study is a pragmatic, single-blind multicentre superiority randomized controlled trial with four arms: CR, PE, EMDR, and WL. Therapy in all three active arms will be delivered over 16 sessions by trained therapists working in routine mental health services. All groups receive TAU for psychosis and will be assessed at T0, T2, T3, T6. Participants in the WL condition receive therapy of choice after T6.

#### **Study Objectives**

#### Primary objective

The primary objective is to compare the effects of CR, PE, and EMDR to WL on researcherrated severity of PTSD symptoms (CAPS-5 total score) over time from baseline to 6-month follow-up.

#### Secondary objective

Secondary objectives are to compare the effects of CR, PE, EMDR, to WL for researcherrated severity of PTSD symptoms at the separate time-points (i.e. mid-treatment, posttreatment, and at 6-month follow-up) and to test the effects (over time and at each timepoint) for clinician-rated presence of PTSD diagnosis according to the DSM-5 criteria, and self-reported severity of complex PTSD symptoms.

#### Tertiary objectives

In addition, we will explore the effects of the treatments on disruption of social functioning by PTSD symptoms, post-traumatic cognitions, dissociation, depression symptoms, paranoid ideation, presence and impact of voice-hearing, social functioning, personal recovery, adversities, experienced resilience, and revictimization over time and at each time-point.

An overview of each outcome variable, corresponding measure, and outcome type is provided in Table 1.

Table 1.	Outcome	variables	and	corresponding	measures	for	primary,	secondary
and tert	iary objecti	ives						

Outcome variables	Measure	Type (continuous or dichotomous)
PTSD symptoms		
Researcher-rated PTSD symptom severity	CAPS-5 	С
PTSD diagnosis	CAPS-5 	D
Self-reported PTSD symptom severity	PCL-5 	С
Self-reported complex PTSD symptom severity	ITQ 	С
Post-traumatic cognitions	PTCI-9 ₅	С
Disruption of social functioning by PTSD	ITQ 	С
symptoms		
Dissociation	TSDQ-s 	С
Psychosis symptoms		
Frequency of voice-hearing	PSYRATS-AHRS-	С
	FRQ 	
Impact of voice-hearing	VIS 	С
Paranoid thoughts	R-GPTS 	С
Depression symptoms	BDI-II 	С
Social functioning	Adapted TUS 	С
Personal recovery	QPR 	С
Adversities	TAEQ 	С
Revictimisation	Interpersonal	С
	victimisation items	
	of the TALE 	
Resilience	BRS 	С

Note: CAPS-5 = Clinician-Administered PTSD Scale for DSM-5; PCL-5 = PTSD Checklist for DSM-5; ITQ = International Trauma Questionnaire; PTCI-9 = Brief version of the Posttraumatic Cognitions Inventory; TDSQ-s = Trait State Dissociation Questionnaire – short version; PSYRATS = Psychosis Symptom Rating Scale – Auditory Verbal Hallucinations Scale; VIS = Voice Impact Scale; R-GPTS = Revised version of the Green et al Paranoid Thoughts Scale; BDI-II = Beck Depression Inventory II; Adapted TUS = Adapted Time Use Survey; QPR = Questionnaire about the Process of Recovery; TAEQ = TTIP Adverse Events Questionnaire; TALE = Trauma and Life Events; BRS = Brief Resilience Scale .

# Randomisation and Blinding

Participants are randomized by an independent researcher using a randomization programme (http://www.randomizer.org) with a 1:1:1:1 allocation ratio, stratified by trial therapist. The allocation sequence is saved in a protected folder to which the research team has no access. The independent researcher informs the therapist of the allocation who in turn informs the participant.

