## Primary Outcome Analysis

To evaluate changes in researcher-rated PTSD symptom severity over time and treatment differences, a LMM will be fitted using restricted maximum likelihood (REML) estimation. The primary model includes baseline scores as covariate, treatment condition as fixed effect, time as categorical variable, an interaction term between treatment condition and time, and a random intercept for each participant to account for within-subject correlations. An interaction effect between treatment condition and time variables would indicate differential treatment effects over time. To appropriately model the within-subject correlation of repeated outcome measures across unequally spaced timepoints, an unstructured covariance matrix will be applied to the residuals in the LMM. This results in the following model equation:

$$Y_{ij} = \beta_0 + \beta_1 \cdot Baseline_i + \sum_{k=1}^{3} \beta_{2k} \cdot Group_{ik} + \sum_{l=1}^{3} \beta_{3l} \cdot Time_{jl} + \sum_{k=1}^{3} \sum_{l=1}^{3} \beta_{4kl} \cdot (Group_{ik} \times Time_{jl}) + u_i + \varepsilon_{ij}$$

Where:

- *Yii*: Outcome for participant *i* at timepoint *j*
- *Baseline*i: Baseline outcome value for participant *i*
- *Groupik*: Dummy-coded treatment condition indicators (3 dummies: CR, PE, EMDR; WL = reference)
- *Timejl*: Dummy-coded time indicators (3 dummies: midtreatment, posttreatment, 6-month follow-up; baseline = reference)
- $Group_{ik} \times Time_{il}$ : Group-by-time interaction terms
- $u_i$ : Random intercept for participant i
- $\varepsilon_{ii}$ : Residual error
- Fixed effects:
  - Intercept  $\beta_0$ : Mean outcome at baseline for WL
  - $\circ$   $\beta_1$ : Effect of individual baseline outcome value (covariate)
  - $\circ$   $\beta_{2k}$ : Group main effects at baseline, compared to WL
  - $\circ$   $\beta_{3l}$ : Time effects for WL (how outcomes change over time within WL)
  - $\circ$   $\beta_{4kl}$ : Additional group-specific changes over time relative to WL

To quantify the magnitude of treatment effects, effect sizes will be estimated for timepoints T3 and T6 based on the mean pre-post change (i.e. baseline scores vs. follow-up scores) of the treatment condition minus the mean pre-post change of WL, divided by the pooled pretest standard deviation 

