## Secondary and Tertiary Outcome Analyses

For continuous outcomes, LMMs with similar methodology as the primary outcome analysis will be applied. For dichotomous outcomes (e.g., clinician-rated presence of PTSD diagnosis) generalized linear mixed models (GLMMs) with a logit link function will be used, in line with the following model equation:

$$\log\left(\frac{\Pr(Y_{ij}=1)}{1-\Pr(Y_{ij}=1)}\right) = \beta_0 + \beta_1 \cdot Baseline_i + \sum_{k=1}^3 \beta_{2k} \cdot Group_{ik} + \sum_{l=1}^3 \beta_{3l} \cdot Time_{jl} + \sum_{k=1}^3 \sum_{l=1}^3 \beta_{4kl} \cdot (Group_{ik} \times Time_{jl}) + u_i + \varepsilon_{ij}$$

Here, the left-hand side of the model equation indicates the log-odds of the outcome being 1 (e.g., no longer meeting PTSD diagnosis criteria).

The trial protocol specified Generalised Estimating Equations (GEE) would be used to analyse dichotomous outcomes. This plan has been updated to employ GLMMs, as they allow explicit modeling of random effects and individual-level variability, while offering more robust performance when handling missing data under missing at random (MAR) assumptions, which better suits our study's anticipated data structure.

Similar to the primary analysis, effect size of continuous outcomes will be estimated with  $d_{ppc2}$ . For dichotomous outcomes, odds ratios (ORs) will be calculated from the fitted GLMM. Here, exponentiated model coefficients will be interpreted as odds ratios comparing the odds of the outcome between treatment arms and timepoints.

In addition to testing treatment effect on primary and secondary outcomes over time, post-hoc pairwise comparisons between treatment groups and the waitlist control group will be conducted at each timepoint using estimated marginal means with Bonferroni correction to adjust for multiple comparisons.

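### Randomisation is stratified by trial therapist but no analysis model contains therapist; if therapists differ, the standard errors will not reflect the design, in a direction the SAP does not let one determine

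*SAP*

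**What the plan says.** SAP, Randomisation and Blinding: participants are allocated "with a 1:1:1:1 allocation ratio, stratified by trial therapist". Study Design: "Therapy in all three active arms will be delivered over 16 sessions by trained therapists working in routine mental health services", while "Participants in the WL condition receive therapy of choice after T6".

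SAP, Primary Outcome Analysis: "The primary model includes baseline scores as covariate, treatment condition as fixed effect, time as categorical variable, an interaction term" of condition with time, and "a random intercept for each participant to account for within-subject correlations". The equation is written out term by term: baseline, three group dummies, three time dummies, their products, a participant intercept and a residual. Therapist is absent.

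SAP, Secondary and Tertiary Outcome Analyses: "For continuous outcomes, LMMs with similar methodology as the primary outcome analysis will be applied". For dichotomous outcomes "generalized linear mixed models (GLMMs) with a logit link function will be used", with the same linear predictor. The Sensitivity Analyses section lists a per-protocol analysis and multiple imputation only. The LMM for adversities and revictimisation under Safety Analysis adds no therapist term. No reason is given for leaving therapist out.

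**The concern.** The factor used to stratify randomisation would normally appear in the analysis. Here it may act in two ways that pull in opposite directions.

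(a) *A therapist level shared by all arms.* Stratification takes differences between therapists' caseloads out of the arm contrasts, to the extent that arms are balanced within therapist. A model without therapist leaves that variation in the residual. Standard errors are then too large and power is lost.

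(b) *Therapist-by-condition variation.* Suppose the stratum therapist also delivers the therapy, and therapists differ in how well they deliver a given one. Patients who share therapist and active arm then have correlated outcomes. WL participants receive no trial therapy before the last assessment, so nothing corresponds to this in WL. A model without the term gives standard errors that are too small.

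What is at stake is the size of every confidence interval and p-value for therapy against WL, across primary, secondary and tertiary outcomes.

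**Working it through.** **Inputs from the SAP.** Two-sided alpha 0.05, power 0.80, effect size 0.5, correlation 0.45, three follow-ups, 20% attrition, 50 per arm (Sample Size Calculation; General principles).

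**Assumed, because the SAP does not give them.** Number of therapists T = 10 or 20; therapist variance share 0.05 or 0.10 of a unit outcome variance.

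**The SAP's own figure.** 2 × ((1.96 + 0.8416)/0.5)² = 62.79. The repeated-measures factor is (1 + 2 × 0.45)/3 = 0.6333, and 62.79 × 0.6333 = 39.77, so 40. Then 40/0.8 = 50 per arm, 200 in total. The stated size reproduces exactly, with no therapist allowance in it.

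**(a) Shared therapist intercept omitted, arms balanced within therapist.** Model SE over true SE = 1/√(1 − ICC). Type I error = 2(1 − Φ(1.96 × ratio)).
- ICC 0.05: ratio 1.026, type I error 4.4%.
- ICC 0.10: ratio 1.054, type I error 3.9%.

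Second basis: therapist variance as a share of single-visit variance, three visits averaged, so the outcome variance is 0.6333. True over model SE = √((0.6333 − share)/0.6333).
- Share 0.05: 0.960, type I error 4.1%. Power with 40 per arm is 81.2% without therapist and 83.3% with it.
- Share 0.10: 0.918, type I error 3.3%. Power is 82.3% without and 86.5% with.

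Simulation on this basis (20,000 runs per setting, four arms of 40, 10 or 20 therapists) gave 4.2% to 4.4% at share 0.05 and 3.1% to 3.5% at 0.10 without therapist, and 4.8% to 5.3% with it.

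**(b) Therapist-by-condition clustering omitted, 50 per arm.** With m = 50/T patients per therapist and arm, the active-arm design effect is DE = 1 + (m − 1) × ICC. The true over modelled variance of an active-versus-WL contrast is (DE + 1)/2, as WL is not clustered in this way. Type I error = 2(1 − Φ(1.96/√ratio)).

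| T | m | ICC | DE | Variance ratio | Type I error |
|---|---|---|---|---|---|
| 10 | 5 | 0.05 | 1.20 | 1.10 | 6.2% |
| 10 | 5 | 0.10 | 1.40 | 1.20 | 7.4% |
| 20 | 2.5 | 0.05 | 1.075 | 1.0375 | 5.4% |
| 20 | 2.5 | 0.10 | 1.15 | 1.075 | 5.9% |

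With 10 therapists the true variance is 10% to 20% larger than modelled. Put the other way, the modelled variance is 9% to 17% too small (1 − 1/1.10; 1 − 1/1.20).

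**Both components present, each of size v, 50 per arm.** True contrast variance = (1 − 2v)/50 + v/T + (1 − v)/50. The SAP's model assumes 2/50 = 0.040. A model with a therapist intercept only assumes 2(1 − v)/50.

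| T | v | True variance | Type I error, SAP model | Type I error, intercept only |
|---|---|---|---|---|
| 10 | 0.05 | 0.0420 | 5.6% | 6.2% |
| 10 | 0.10 | 0.0440 | 6.2% | 7.6% |
| 20 | 0.05 | 0.0395 | 4.9% | 5.5% |
| 20 | 0.10 | 0.0390 | 4.7% | 6.0% |

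Simulation of the two 10-therapist rows (8,000 runs, therapist as a fixed effect) gave 5.9% against 6.5%, and 6.9% against 8.5%.

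**The case against.** The omission itself is not in dispute: the models are written out in full, so it cannot be read as a detail left to the protocol. The case against concerns how much follows from it.

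- *Everything numerical is assumed.* This stands. With no therapist variance, nothing changes. With 40 therapists and 40 analysable per arm (one patient per therapist and arm), mechanism (b) vanishes and type I error is 5.0%. With 20 therapists and both components present, the SAP's model is close to nominal.
- *The ICC that matters is conditional on baseline.* This stands. The model already adjusts for baseline, which may absorb some therapist variation.
- *Balance within therapist is not assured.* This stands. The SAP mentions no blocking. Small strata shared among four arms may be uneven, and mechanism (a) then shrinks.
- *Nothing says outright that the stratum therapist delivers the therapy.* It is the natural reading of Study Design with Randomisation and Blinding, but it remains an assumption. Mechanism (b) depends on it; (a) does not.
- *Mechanism (a) costs power, not validity.* This stands.
- *Adding only an intercept can do harm.* This stands and shapes the fix. The intercept removes the conservative error and leaves the anti-conservative one.

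A reader might infer that the planned tests are invalid or inflate type I error. The SAP does not support that: it gives neither the number of therapists nor an ICC, and the net error may be in either direction. A reader might also infer that 50 per arm is wrong. It reproduces on its own inputs, and a shared therapist intercept does not call for more participants.

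**Conclusion.** The point holds as a conditional one. The SAP stratifies by trial therapist and omits therapist from every model it specifies, so the standard errors do not reflect the design if therapists differ. Neither the direction nor the size can be settled from the document. On the assumptions above, type I error for a therapy-versus-WL contrast lies between about 3.3% (shared intercept only, share 0.10, visits averaged) and 7.4% (therapist-by-condition only, 10 therapists, ICC 0.10), and it is nearer to 5% when both are present. The discrepancy is modest over most of that range. It should be put right before analysis, because the change is cheap and a later choice between models with different standard errors would be open to question. It is not a ground for calling the primary analysis invalid.

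**What to change.** 1. Add trial therapist (the randomisation stratum) as a random intercept to the primary LMM, to the secondary and tertiary LMMs, including the one for adversities and revictimisation, and to the GLMM. A random effect is preferable to fixed effects if strata are small.
2. Specify with it a therapist-by-condition random effect for the three active arms. Put it in the primary model where it can be estimated; otherwise make it a pre-specified sensitivity analysis reported beside the primary result.
3. State the fallback if a variance component is estimated at zero or the model does not converge, including the order in which terms are dropped.
4. If therapist is to be left out after all, give the reason.

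Cost: SAP wording and two model terms. No new data should be needed, since the stratum was required to randomise each participant, WL included. The sample size need not change for the intercept. The risks are zero variance estimates or non-convergence, which item 3 covers, and more anti-conservative tests if item 1 is adopted without item 2 and therapist-by-condition variance exists.

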## Sample Size Calculation

A formal power analysis was conducted to determine the required sample size for the planned longitudinal intention-to-treat (ITT) analyses using linear mixed models (LMM).

Based on data from previous randomized controlled trials in this field , the calculation used the following parameters: significance level ( $\alpha$ ) of 0.05 (two-sided), power (1- $\beta$ ) of 0.80, expected correlation between repeated measures ( $\rho$ ) of 0.45, and 3 repeated follow-up assessments. The minimum detectable effect size was set at 0.5 (medium effect, compared to waiting list control), while accounting for an anticipated attrition rate of 20%. These calculations indicated that 50 participants would be needed in each study arm. Therefore, our aim will be to randomize a total of 200 participants.

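### The stated 80% power belongs to a time-averaged therapy-versus-waitlist contrast that the primary analysis never defines

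*SAP*

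**What the plan says.** **Objective.** The SAP's primary objective is to compare each of the three therapies with WL on CAPS-5 severity "over time from baseline to 6-month follow-up". Effects at separate time points are a secondary objective.

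**Sample size.** The Sample Size Calculation says that it serves the planned longitudinal mixed-model analyses. Its inputs are a significance level "of 0.05 (two-sided"), power "of 0.80, expected correlation between repeated measures" "of 0.45, and 3 repeated follow-up assessments", an effect size ("The minimum detectable effect size was set at 0.5 (medium effect, compared to waiting list control"), and 20% loss ("while accounting for an anticipated attrition rate of 20"). The result is: "These calculations indicated that 50 participants would be needed in each study arm". It does not say which contrast is powered, or whether 0.5 applies at each visit, at one visit or on average.

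**Analysis.** The Primary Outcome Analysis fits condition, time and their interaction. Baseline enters both as a covariate and as the reference level of a four-level time factor. One sentence gives a term an inferential reading: "An interaction effect between treatment condition and time variables would indicate differential treatment effects over time". No contrast averaged over follow-ups is defined. The Secondary and Tertiary Outcome Analyses section adds Bonferroni-corrected comparisons with WL at each visit and calls them post hoc.

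**The concern.** A power statement should describe the test on which the trial will be judged. Here the sample size identifies one contrast, and the primary analysis points the reader to another term without committing to it. The two respond differently to the same benefit. A therapy that improves CAPS-5 early and holds the gain gives a clear average difference from WL. The interaction spreads that effect over several degrees of freedom, and it has no signal at all if it runs only over the follow-up visits.

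At stake is whether the primary objective has a fixed test with known power before the data are analysed, or whether the choice between an average difference, an interaction and a set of per-visit comparisons stays open.

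**Working it through.** **Inputs from the SAP (Sample Size Calculation):** two-sided alpha 0.05; power 0.80; correlation between repeated measures rho = 0.45; 3 follow-ups; effect d = 0.5, in SD units; attrition 20%.

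**Assumptions not in the SAP:** the effect at each of T2/T3/T6, and the correlation r between baseline and each follow-up. Both are varied below. SD is 1 at every visit, and 40 per arm are analysed.

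**1. Reproducing 50 per arm.** The variance of the mean of three follow-ups is (1 + 2 × 0.45)/3 = 0.6333.

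n = 2 × (1.960 + 0.842)² × 0.6333 / 0.5² = 39.77, so 40 analysed per arm, and 40/0.8 = 50 randomised. Power at 40 is 80.2%.

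The other usual variants, with r = 0.45 and the same attrition, do not give 50:

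| Contrast | Variance | Randomised per arm |
|---|---|---|
| Mean of follow-ups, unadjusted | 0.6333 | **50** |
| Single follow-up score | 1 | 79 |
| Single change score | 1.10 | 88 |
| Single visit, baseline-adjusted | 0.7975 | 64 |
| Mean change from baseline | 0.7333 | 59 |
| Mean of follow-ups, baseline-adjusted | 0.4308 | 35 |

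**2. Interaction with baseline as the reference time, as coded.** For one therapy versus WL the test has 3 df. The changes from baseline have covariance S = (1 − rho)I + (1 + rho − 2r)J. The noncentrality is (n/2) v′S⁻¹v, where v holds the three effects. For a constant effect d this is (40/2) × d² × 3/[(1 − rho) + 3(1 + rho − 2r)].

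With r = 0.45: 20 × 0.25 × 3/2.2 = 6.82, and power is 57.7%. The four-arm test on 9 df has noncentrality 0.75 × 40 × 0.25 × 3/2.2 = 10.23 and power 57.6%.

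3-df power when r varies, constant effect 0.5:

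| r | Noncentrality | Power |
|---|---|---|
| 0.2 | 4.05 | 36% |
| 0.3 | 4.84 | 43% |
| 0.45 | 6.82 | 58% |
| 0.6 | 11.54 | 82% |

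3-df power when the profile varies, r = 0.45:

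| Effect at T2/T3/T6 | Noncentrality | Power |
|---|---|---|
| 0.25/0.5/0.25 | 4.55 | 40% |
| 0.25/0.5/0.5 | 6.25 | 54% |
| 0.5/0.5/0.5 | 6.82 | 58% |
| 0/0.5/0.5 | 9.09 | 72% |
| 0.25/0.5/0.75 | 11.36 | 82% |

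**3. Interaction over follow-ups only.** If the T0 rows are left out, so that baseline is only a covariate, the interaction asks whether the effect differs between T2, T3 and T6. For a constant effect the noncentrality is 0, and power equals alpha, 5%.

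**4. Baseline-adjusted average over T2, T3 and T6.** The variance is 0.6333 − r², and the standard error is √(2 × variance/40).

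| Profile | r | Mean effect / SE | Power, alpha 0.05 | Power, alpha 0.05/3 |
|---|---|---|---|---|
| Constant 0.5 | 0.45 | 0.5/0.1468 = 3.41 | 92.6% | 84.4% |
| Constant 0.5 | 0.2 | 0.5/0.1722 = 2.90 | 82.7% | 69.5% |
| 0.25/0.5/0.5 | 0.45 | 0.4167/0.1468 = 2.84 | 81.0% | 67.2% |

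**The case against.** The strongest reply is that the SAP never makes the interaction its primary test. The sentence on it explains a model term and sets no success criterion. The objective, each therapy against WL over time, fits the averaged contrast that the sample size powers, and for that contrast 200 is enough under the stated inputs. This stands in part. A reader might infer that the trial has chosen an underpowered test, and the document does not support that. But if the interaction is not the test, no other test of the primary objective is written down.

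A reader might also take 58% as the power implied by the plan's own inputs. It is not: the plan gives neither an effect profile nor a baseline-to-follow-up correlation. T2 is mid-treatment, at 7 weeks, so a full effect there is not an obvious default.

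Nor can the 5% figure be read as the power of the plan as written, since the written model codes baseline as the reference time. It shows what would follow if the double use of baseline were resolved by dropping the T0 rows.

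Finally, a benefit would not go wholly untested. Per-visit comparisons with WL are planned, as are effect sizes at T3 and T6. But the comparisons are post hoc and serve a secondary objective, so they do not supply the primary test.

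**Conclusion.** The concern holds as a mismatch between the powered contrast and the primary analysis. The arithmetic behind 50 per arm is exact, and of the variants tried only the time-averaged, baseline-unadjusted contrast yields it. The primary analysis does not define that contrast, so the 80% is not a property of any test in the plan.

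The size of the gap depends on assumptions that the plan does not state. With baseline as a time level and 40 per arm, the interaction's power is about 58% in the constant-effect case at r = 0.45, within a range of about 36% to 82%. A reader might conclude that the sample is too small; these results do not show that. What they show is that the test must be fixed and the power stated for it.

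**What to change.** **Primary Outcome Analysis.** Name the primary test as three contrasts, one per therapy versus WL: the baseline-adjusted difference averaged over T2, T3 and T6, estimated from the mixed model. Call the interaction descriptive. Decide whether baseline is a covariate or a response level, and make the time coding and coefficient definitions agree with that choice.

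**Sample Size Calculation.** Say that the time-averaged therapy-versus-WL difference is the powered contrast. Restate its power at 40 evaluable per arm with the assumed effect profile, baseline correlation and alpha, as a range. For a constant 0.5 effect and baseline correlation 0.2 to 0.45, that is about 83% to 93% at alpha 0.05 and about 69% to 84% at 0.05/3. Add that it is lower if the T2 effect is smaller. If the sponsor keeps the interaction as the criterion, the 80% should be replaced by the interaction's own power range.

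**Cost.** SAP wording only, before the data are analysed, with no change to recruitment. The price is a power statement that openly depends on its assumptions and, at the stricter alpha, may fall below 80%. Weighting the three visits equally is a choice that the sponsor should confirm, because it gives the mid-treatment visit the same say as the later two.
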